The prevalence of CIDP is estimated to be between 1-9 cases per 100,000 (3, 4). However, diagnosis can be difficult and these numbers may be an underestimate of the true prevalence. Nerve conduction studies are specific but over 15 diagnostic criteria have been published in an effort to improve sensitivity (5). One of the possible sources of insensitivity can be low amplitudes which could reflect conduction block rather than axonal loss but cannot be discriminated on nerve conduction studies (6). CSF protein elevation is present in 90% of patients, but can be present in 50% of patients misdiagnosed as CIDP (7) Nerve biopsy is specific, but shows demyelination in only 50-66% of biopsies (8, 9). Teased fiber preparation is technically challenging and not performed routinely at all labs. In addition, none of these methods have proved useful for determining efficacy of treatments. Motor strength and disability scores are nonspecific but have been the primary endpoint measures used in CIDP studies. No tool currently exists for identifying demyelination in CIDP as either a diagnostic test or to assess treatment effect. This hypothesis-generating study will assess whether skin biopsy can discriminately identify demyelination in CIDP patients from healthy controls and other neuropathies such as diabetes mellitus. In addition, because skin biopsies can be repeated over time, this study will assess whether this biomarker is responsive to treatment, which has not been shown with any previous biomarker.

As mentioned, glabrous skin biopsy affords a method of pathological assessment of distal nerves which is minimally invasive and repeatable. Saporta et al published evidence of segmental demyelination in CIDP patients in skin biopsy using them as controls for an inherited neuropathy study (10). Segmental demyelination was observed in all four CIDP patients studied. We have used this method to demonstrate abnormalities in myelin and the node of Ranvier in diabetic subjects and healthy controls with average age of 53 (35-75). We observed 5% segmental demyelination in healthy controls and 7.3% in type 1 diabetic patients, 7.7% in type 2 diabetic patients (11). We propose to use this technique to study patients diagnosed with CIDP to evaluate its usefulness as a potential diagnostic tool and as a biomarker of treatment efficacy. We expect to observe a significantly higher percentage in CIDP than our previous diabetic

patients which will allow us to differentiate CIDP from diabetes and healthy aged controls. In addition, we expect to see demyelination improve after IVIg treatment with Privigen. In addition, we suggest that nodal architecture will be abnormal in CIDP compared to our data in healthy control patients.

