Aim 1. We will obtain glabrous skin biopsies in 10 CIDP patients to demonstrate increased percentage of myelinated fibers with segmental demyelination using immune-histochemical labeling of myelin and axonal proteins compared to those of historical healthy control and diabetic subjects. We will demonstrate that this method will be able to discriminate CIDP patients from healthy controls and diabetic neuropathy patients.

Aim 2. We will perform follow up biopsies 3 months and 6 months after treatment to demonstrate whether there is decreased segmental demyelination after treatment.

Aim 3. We will compare measurement of segmental demyelination in vivo to medical research council (MRC) scores for muscle strength for each patient.

The overall goal is to provide preliminary data for a future study to demonstrate using SClg and IVIg is efficacious in preventing in vivo segmental demyelination and that this correlates with improvement in patient outcomes.

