Analysis of segmental demyelination: Measurement of myelinated fiber density from glabrous skin biopsies will be calculated according to methods of previous publication (7, 23, 24). Meissner corpuscle density will also be performed for comparison. Number of papillary, dermal internodes will be calculated. Analysis of nodes of Ranvier will include quantitation of nodes with greater width (> 6 µm; (25)); branching at nodes, localization of ion channels within nodes will be quantified from 25 nodes from each biopsy, using at least 3 sections to ensure random distribution. Given the previous normal healthy control data demonstrating a 5% rate for healthy controls and 7.7% in diabetic subjects, 20% will be used as the cutoff for CIDP. 15.7% was the 95th percentile observed in both diabetic and healthy controls, with one diabetic subject having a 15% demyelination rate. Given that [name] observe demyelination in multiple fibers from previous CIDP patients sampled, we believe this will ensure diagnostic efficiency with sufficient sensitivity (9). It is unknown what treatment effects we will find, but given the standard deviation was 4.1% in the previous study, we would expect a change greater than 5% to be meaningful.

Further characterization of nodal and internodal integrity for aim 1 will be investigated with nodal staining using pan-sodium channels (7), the paranodal staining of Contactin-associated protein (Caspr; Neuromab) and internodes will be labeled by staining for myelin basic protein (MBP). These will be helpful to further measure nodal width and alsoand to evaluate for decompartmentalization of ion channels which channels, which could contribute to conduction block. An internode will be defined as a segment with intact MBP, Pan-Na and PGP9.5 staining demonstrating a node on each end. A total number of nodes per biopsy (in 4 sections) will be calculated. We will estimate segmental demyelination percentage by calculating numbers of fibers with demyelination (identified as gaps of MBP stain within a fiber where MBP stain is visible on both sides of gap and PGP 9.5 stain is present confirming axonal integrity)/total number of fibers counted (25). Repeated measures for each patient will be calculated to determine if there is decrease in segmental demyelination over time after treatment.

IVIg infusions:

Protocol Version #8:

9

Protocol Date:

10/04/2022

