10.0 Statistical Considerations

As this is a pilot study and has never been performed in this population, a formal power calculation has not been performed. A sample of 10 CIDP patients was deemed appropriate to determine if abnormal dermal myelinated pathology exists which can be evaluated in further studies. It is possible patients may have insufficient pathology. This study will provide data for future studies and will enable power calculations. Morphometric analysis of IENF, myelin thickness, intermodal length, etc will be compared using nonparametric Wilcoxon test of means of CIDP patients and healthy controls collected from previous study (18).

The data collected from Aim 1 will also be used for both Aims 2 and 3. The primary outcome measures for segmental demyelination obtained from biopsy will include the number of fibers with segmental demyelination (out of a random sample of 25 fibers), the average length of demyelinated segments, and the number of fibers with sodium channel spreading over denuded axons. As a secondary outcome, clinical outcomes such as MRC scores from the routine standard of care will be also collected.

For Aim 2, signed rank tests will be used to test whether there would be any improvement after treatment in the primary outcomes measured at 3 months and 6 months separately, compared to those measured at the baseline. Also, the outcome measures obtained from confocal vs. fluorescence alone will be compared to examine whether the measurements are similar using a random-effects model along with application of bioequivalence testing methodology.

For Aim 3, to examine whether the primary outcomes and MRC scores are correlated, their correlations will be compared using Spearman rank correlations at 3 months and 6 months separately.

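### Aim 1 promises per-patient discrimination of CIDP, but the only between-group analysis in Section 10 tests a group shift, and the 20% cutoff is not tied to the Aim 1 conclusion

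*Protocol*

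**What the plan says.** **The inference.** The last sentences of the Background, just before Section 2.0, read "We expect to observe a significantly higher percentage in CIDP than our previous diabetic" and continue "patients which will allow us to differentiate CIDP from diabetes and healthy aged controls". Differentiation is presented as following from a significantly higher group percentage.

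**The aim.** Aim 1 in Section 2.0 goes from showing an increased percentage to "We will demonstrate that this method will be able to discriminate CIDP patients from healthy controls and diabetic neuropathy patients".

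**The analysis.** Section 10.0 lists several morphometric measures, ending in an open-ended et cetera, which "will be compared using nonparametric Wilcoxon test of means of CIDP patients and healthy controls" from an earlier study. Segmental demyelination is not named in that list, and no comparison with diabetic subjects is named. The other tests in Section 10.0 serve Aims 2 and 3 and the confocal comparison.

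**Classification elsewhere.** Section 6.0, under the analysis of segmental demyelination, states that "20% will be used as the cutoff for CIDP" and expects sufficient sensitivity from it. The microscopy text in the same section mentions ROC curves, but only for additional measures that may be generated. Section 10.0 uses neither.

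**The concern.** The question is diagnostic: given one patient's biopsy, can that patient be told apart from a healthy or diabetic person? The Wilcoxon test has equal distributions in the two groups as its null. Rejecting it says that the groups differ. It does not say how many patients fall on the right side of a threshold.

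Followed as written, the plan could report a significant group difference and describe it as discrimination while most CIDP biopsies lie below the protocol's own cutoff. The protocol exists to supply data for later studies. Those studies need an estimate of sensitivity and specificity, and Section 10.0 does not call for one.

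**Working it through.** The protocol states no power or sample-size figure, so there is none to reproduce. The check asks whether a significant group test and a low yield at the cutoff can occur together on the protocol's own figures.

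**Inputs from the protocol**
- CIDP patients: 10 (Section 10.0, "A sample of 10 CIDP patients was deemed appropriate").
- Control means: 5% and 7.7% (Section 6.0, "demonstrating a 5% rate for healthy controls and 7.7% in diabetic subjects").
- SD: 4.1 points (Section 6.0, "given the standard deviation was 4.1% in the previous study"; the group is not specified).
- Cutoff: 20%, which is 5 of the 25 fibers sampled per biopsy.

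**Assumptions (not in the protocol)**
- Two-sided 0.05.
- 10, 20 or 40 historical controls.
- CIDP means of 10–16%, with CIDP SD 4.1, or 6.0 as a variation.
- Normal data, or 25-fiber binomial counts as a variation.
- The Wilcoxon is applied to segmental demyelination and also run against diabetic subjects, which Section 10.0 does not state.

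**Step 1: share of CIDP patients reaching the cutoff.** Share = 1 − Φ((20 − mean)/SD). At mean 14%: (20 − 14)/4.1 = 1.46, so 7.2%. At 15%: 5/4.1 = 1.22, so 11.1%. At 16%: 4/4.1 = 0.98, so 16.5%.

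**Step 2: rejection rate.** Simulated two-sided rank-sum tests, 4,000 runs per setting. The null check gave 4.0–4.9%. Rates are for 10/20/40 controls.

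| CIDP mean (SD 4.1) | Reach 20% | Reject vs diabetic (7.7%) | Reject vs healthy (5%) |
|---|---|---|---|
| 10% | 0.7% | 19/26/32% | 69/83/90% |
| 12% | 2.6% | 55/70/80% | 93/98/99.8% |
| 14% | 7.2% | 88/96/98% | 99.3/99.9/100% |
| 15% | 11.1% | 94/99/99.8% | 99.8/100/100% |
| 16% | 16.5% | 98/99.7/100% | 100/100/100% |

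**Step 3: less favourable models at a CIDP mean of 15%**
- CIDP SD 6.0: 20% reach the cutoff; rejection is 81/90/95% against diabetic subjects and 98/99/99.9% against healthy controls.
- 25-fiber binomial: 32% reach 5 of 25; rejection is 66/78/87% against diabetic subjects and 94/99/99% against healthy controls.

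**Step 4: the other direction.** With SD 4.1 and a CIDP mean of 25%, (20 − 25)/4.1 = −1.22 and sensitivity is about 89%. At 30% it is about 99%.

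**Step 5: AUC and cutoff answer different questions.** AUC = Φ((15 − 7.7)/√(4.1² + 4.1²)) = 0.90 against diabetic subjects at a CIDP mean of 15%, although only 11% of patients reach 20%. A low yield at 20% may therefore reflect the position of the cutoff and not a weak marker. The group test cannot tell these apart.

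**Step 6: what 10 patients can show.** Exact 95% intervals for sensitivity are 69.2–100% for 10/10, 44.4–97.5% for 8/10 and 18.7–81.3% for 5/10.

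**The case against.** The strongest reply is that the protocol contains no rule making a significant Wilcoxon test the criterion for Aim 1. The Background sentence is an expectation, and the study calls itself hypothesis-generating. A per-patient cutoff is prespecified for the key measure, ROC curves are mentioned, and each patient's percentage will be recorded, so sensitivity could be read from the data. Interval methods are commonly left to an SAP.

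Much of this stands, and it limits what can be claimed. A reader might infer any of the following, and the protocol does not support them:
- **A formal success rule.** None is written, and segmental demyelination enters the Wilcoxon list only through its et cetera.
- **That the test would reject almost always.** Against diabetic subjects it rejects in 19–80% of runs at CIDP means of 10–12%.
- **Inflated type I error.** The high rates above are power against a true difference. Under the null the rate is 4.0–4.9%.
- **That most patients will be missed.** This follows from choosing CIDP means below 20%. The protocol reports demyelination in all four CIDP patients studied earlier and expects a clear separation.
- **That classification is ignored.** It is not; it is left unconnected to Aim 1's conclusion.

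The reply does not remove the mismatch. The protocol itself writes the step from group difference to differentiation and promises to demonstrate discrimination, yet its statistical section links Aim 1 to no classification analysis. The ROC provision concerns other measures. A pilot excuses low precision, but not a conclusion of a different kind from the analysis. Nor can a CIDP mean below 20% be ruled out: Section 10.0 concedes that pathology may be insufficient, and Section 4.0 admits patients already treated for up to 6 months.

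**Conclusion.** The point holds as a mismatch between claim and analysis. The analysis in Section 10.0 can show that CIDP patients differ as a group from healthy controls. It cannot by itself support the claim that biopsy discriminates CIDP patients, and for diabetic subjects no comparison is stated at all.

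The size is conditional. With SD 4.1 in both groups, two-sided 0.05, 10 to 40 controls and a true CIDP mean of 14–16%, rejection against diabetic subjects is about 88–100% while 7–17% of patients reach the cutoff. A larger SD or binomial noise weakens the contrast without removing it. Lower means reduce the chance of rejection, and means well above 20% give high sensitivity. Because the CIDP mean, CIDP SD and number of controls are not given, these figures show what can happen and do not predict the result.

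**What to change.** - **Section 10.0:** base Aim 1's discrimination conclusion on baseline segmental demyelination classified at the 20% cutoff. Report sensitivity in CIDP with an exact 95% CI, specificity separately in the historical healthy and diabetic groups with exact CIs, and AUC with a CI against each group. State whether exactly 20% counts as positive, since 5 of 25 fibers falls on the boundary.
- **Wilcoxon test:** keep it as evidence of a group difference only, name segmental demyelination as an outcome, and say whether diabetic subjects are compared.
- **Background and Aim 1:** replace the promises to differentiate and to demonstrate with wording about estimating discrimination, so that a significant group difference alone does not support the claim.
- **Specificity:** label it as apparent, because the cutoff was justified from the same historical controls.

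The cost is protocol wording and a few lines of analysis, with no extra visits or biopsies, assuming individual values for both historical groups are still held. The drawback is that the claim becomes an estimate with a wide interval: even 10 of 10 patients above the cutoff leaves a lower limit of 69%.

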2.0 Rationale and Specific Aims

Study Hypothesis and Objectives:

Chronic inflammatory demyelinating polyneuropathy (CIDP) is a chronic, disabling illness where there is immune-modulated demyelination of motor and sensory myelinated axons. Unlike most polyneuropathies, CIDP is treatable, and responds to multiple immunotherapies, the most effective being intravenous immunoglobulin (12). Newer approaches include subcutaneous immunoglobulin (SCIg) which has been used successfully for other patients and has shown promise in the treatment of CIDP (13).

The main treatment of CIDP has been intravenous immunoglobulin (IVIg), typically given in pulses or repeated treatments every 3 to 6 weeks. About 50-70% of patients respond to IVIg treatment (14) as opposed to 40% of patients on prednisolone or 30-88% of patient to plasma exchange, but is difficult to deliver repeatedly (15-17). The goal of immunoglobulins or immunosuppressive therapy is to prevent demyelination which is secondary to autoimmune –mediated damage to peripheral sensory and motor nerves.

The major barrier to treating patients effectively has been identifying correctly patients with CIDP who will respond to immunomodulatory treatment. Nerve conduction studies and nerve biopsy are insensitive at identifying patients with acquired demyelination. Skin biopsy has been used as a diagnostic tool for neuropathies. Biopsy of glabrous skin can be repeated over time and using antibodies to myelin antigens tagged with florescent proteins, can demonstrate demyelination, and abnormalities at the node of Ranvier (gaps in myelin where

Protocol Version #8:

Protocol Date:

10/04/2022

salutatory conduction takes place, important for axon potential propagation in myelinated nerves), in addition to quantifying density of myelinated fibers present, (18, 19). Segmental demyelination has been shown to be present in glabrous skin biopsies of CIDP patients (10) in a previous small study.

We hypothesize that dermal myelinated fibers in glabrous skin biopsies show segmental demyelination in CIDP patients, which will improve over time with treatment.

Aim 1. We will obtain glabrous skin biopsies in 10 CIDP patients to demonstrate increased percentage of myelinated fibers with segmental demyelination using immune-histochemical labeling of myelin and axonal proteins compared to those of historical healthy control and diabetic subjects. We will demonstrate that this method will be able to discriminate CIDP patients from healthy controls and diabetic neuropathy patients.

Aim 2. We will perform follow up biopsies 3 months and 6 months after treatment to demonstrate whether there is decreased segmental demyelination after treatment.

Aim 3. We will compare measurement of segmental demyelination in vivo to medical research council (MRC) scores for muscle strength for each patient.

The overall goal is to provide preliminary data for a future study to demonstrate using SClg and IVIg is efficacious in preventing in vivo segmental demyelination and that this correlates with improvement in patient outcomes.

3.0 Animal Studies and Previous Human Studies

[name] and colleagues demonstrated demyelination in their CIDP samples used as comparison to Charcot-Marie-Tooth Neuropathy patients (Saporta et al.). Quantification of demyelination in these samples was not done as quantitatively as we performed in our diabetes population (Peltier et al.). The work described has never previously been done in the CIDP population. This pilot study will provide data for future larger studies to explore the effect of treatment on demyelination in CIDP.

4.0 Inclusion/Exclusion Criteria

Inclusion Criteria:

1. Adults (age \geq 18 years) with definite or probable CIDP according to the EFNS/PNS criteria may enter the trial within 6 months of treatment onset or treatment naïve patients. Written informed consent is obtained by the local investigator before entry into the study.
2. IVIg treatment of 0.8 up to 1.2 g/kg per 30 days will be allowed up to 6 months. It is expected some patients may be on variable treatment regimens, and as long as they are not significantly declining, efforts will be made to continue treatment regimens already instituted.
3. Prednisone in doses up to 20 mg /day will be allowed as long as dose has been stable for 90 days and is not being escalated or tapered during study.

4. Previous plasma exchange will be allowed as long as it is not continued during the study.

Exclusion Criteria:

1. Other causes of polyneuropathy, multifocal motor neuropathy, diabetes mellitus, alcohol, family history of neuropathy, monoclonal gammopathy or malignancy, history of drug or toxin exposure, which could reasonably cause neuropathy. Coexistent monoclonal gammopathy will also be used as an exclusion as these patients may not have the same response to IVIg.
2. Any other disease that may cause neurological symptoms and signs or that may interfere with treatment or outcome assessments.
3. Severe conditions that may interfere with an evaluation of the study product or satisfactory conduct of the study such as current malignancy or history of allogeneic bone marrow/stem cell transplant, cardiac insufficiency (New York Heart Association Classes III/IV), cardiomyopathy, cardiac arrhythmia requiring treatment, unstable or advanced ischemic heart disease, congestive heart failure or severe hypertension, chronic kidney disease deemed too severe to safely use IVIg, known hyperprolinemia, known bleeding disorders, severe skin disease at the planned injection sites or biopsy site, alcohol, drug or medication abuse.
4. History of keloids or other reactions to local anesthetic making skin biopsies unsafe.
5. Patients with the following laboratory results:
 - a. Positive result at screening on any of the following viral markers: human immunodeficiency virus-1 or 2, or hepatitis B or C virus.
 - b. Abnormal laboratory parameters: creatinine greater than 1.5 times the upper limit of normal (ULN), blood urea nitrogen greater than three times the ULN if the increase is related to potential kidney disease, or hemoglobin less than 10 g/dL
6. Fulfilling the following general criteria: inability to comply with study procedures and treatment regimen; mental condition rendering the patient unable to understand the nature, scope, and possible consequences of the study; pregnancy or nursing mother; intention to become pregnant during the course of the study; female patients of childbearing potential either not using or not willing to use a medically reliable method of contraception for the entire duration of the study or not sexually abstinent for the entire duration of the study or not surgically sterile; participation in another clinical study or use of another investigational medicinal product within the same time period of the study.
7. Additional medications and treatments other than prednisone and IVIg for treatment of CIDP such as azathioprine, mycophenolate, rituximab and ongoing plasma exchange as this will either confound or interfere with effects of IVIg.

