5.0 Enrollment/Randomization

The study will be posted on Clinicaltrials.gov in concordance with guidelines. 20 patients will be recruited by advertisement with a goal of 10 patients completing the study. Patients will be recruited within Vanderbilt University Medical Center and affiliated Neurologists, as well as local neurologists in Alabama, Kentucky, Tennessee and Georgia. Letters will also be sent to academic medical centers close by such as University of Kentucky, University of Tennessee, Emory University, and University of

Protocol Version #8:

Protocol Date:

10/04/2022

Alabama. Advertisements will list the contact information of the PI, as well as ,the research study nurse.

All patients will be contacted by the study nurse after response or in the Vanderbilt Neurology Neuromuscular Clinic. The patients will be given information about the study and a copy of the informed consent to look over. Patients interested in the study will be scheduled for screening visits within the Vanderbilt Clinical Research Center (CRC). At the time of their screening visit they will be consented according to the principles of the Declaration of Helsinki and 2018 Common Rule Requirements.

Within 3 weeks, if a patient is found to be eligible at the time of screening an enrollment visit will be scheduled. All patients will be prospectively entered into the study. No randomization or blinding will take place as this is an observational prospective study utilizing new procedures for a biomarker without change in therapy. All efforts will be made to recruit patients prior to therapy initiation without significantly delaying therapy.

Address for contact information will be Department of Neurology, [name], [name]. Phone number is [contact].

List the process for randomization and/or registration; list the address, phone number or website where the registration will take place.

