6.0 Study Procedures

Day -30 -0, Visit 1: Screening visit:

Procedures:

Consent: Patients will provide written consent according to the principles of the 2018 Common Rule and Declaration of Helsinki

H&P: Detailed history and physical with neurological examination will be performed.

MRC score: Medical Research Council (MRC) score for muscle strength will be performed.

Nerve Conduction Studies: Limbs will be warmed to at least 31 C minimum temperature. Antidromic sensory nerve conduction studies of the sural, median and ulnar nerve will be performed. Motor conduction studies of the peroneal, tibial, ulnar and median with proximal studies and F-waves will be performed. Unless patients have significant asymmetry, all studies will be done on the left. Conduction block and temporal dispersion will be noted.

Labs: Blood will be drawn for CBCPD, IgA, CMP. If previously performed will record CSF protein and cell count.

If patients are found to have history and exam consistent with CIDP, met ENFS criteria (cite), inclusion, exclusion criteria including less than 6 months of treatment for CIDP

Protocol Version #8:

Protocol Date:

10/04/2022

they will be accepted into the study and baseline visit will be scheduled 24 hours to 30 days apart. No randomization will take place as all patients will be treated.

Day 1, Visit 2: Baseline visit:

Patients qualifying for the study will be invited back for baseline visit. If patients have not been on IVIg treatment this visit will be scheduled as soon as possible to avoid delays in treatment. If patients have been started on IVIg treatment, patients will be scheduled the day before their next infusion to approximate a nadir in treatment for best baseline measurement.

Procedures:

Physical exam: Interval history will be taken (if appropriate) and physical exam with neurological examination repeated.

MRC score: MRC score will be documented.

INCAT score: The INCAT score will be collected as a secondary endpoint as it has been used in both ICE and PATH studies (refs). The INCAT score for upper and lower extremities will be documented.

Skin biopsies:

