Treatment naïve patients will be initiated on IVIg treatment after baseline visit procedures are completed. This can occur later that day or within the next 14 days. Patients who are treatment naïve will be given a loading dose of 2 g/kg IV over 3-5 days at standard infusion rates which will take 4-6 hours daily, depending on comorbidities and age. Patients will receive acetaminophen and diphenhydramine as standard pre-infusion prophylactic treatment. Patients will receive Privigen which is FDA approved for CIDP treatment either at Vanderbilt University Medical Center hospital infusion center or outpatient infusion center depending on insurance. Patients will then have 1 g/kg IVIg infusions scheduled every 3 weeks for 6 months. Every attempt will be made to ensure Privigen will be used for IVIg product as it is FDA approved for CIDP, is temperature stable, and has no sucrose (26). No placebo will be used given this would be unethical. Patients will serve as their own controls, and the hypothesis is that percentage of segmental demyelination found should decrease as INCAT score and strength increases.

For patients previously treated:

Baseline visit will be arranged closest to the day prior to infusion to ensure the best possible baseline measurement. They will resume according to the patient's previous schedule. Patients will have up to 1.2 g/kg monthly to account for different patient management schedules and variation and patients will be on Privigen ideally.

Patients with escalating weakness not responding to IVIg will be allowed to try additional treatments but will be released from study. Additional treatment with prednisone up to 20 mg/day will be allowed but must be stable dosing and not escalating to avoid additional variability.

Patients will receive IVIg infusions q3 weeks. A monthly phone call will occur so the coordinator can confirm that patients are doing well, having no new treatment related side effects, and are receiving IVIg infusions either at home or in infusion centers.

Day 90, Visit 3:

Procedures (previously described):

History & Physical Exam: Note interval history.

MRC Score

INCAT Score

Skin Biopsy

Labs: BMP to check renal function

Day 180, Visit 4:

Procedures (previously described):

History & Physical Exam: Note interval history.

MRC Score

INCAT Score

Skin Biopsy

Labs: BMP to check renal function

Nerve conduction studies will be repeated from Baseline visit 1

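### The IVIg ceiling of 1.2 g/kg per 30 days for previously treated patients lies below the protocol's own maintenance regimen of 1 g/kg every 3 weeks (1.43 g/kg per 30 days)

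*Protocol*

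**What the plan says.** Protocol Section 4.0, inclusion 1, admits patients who are treatment-naive or within 6 months of starting treatment. Inclusion 2 then sets the dose range: "IVIg treatment of 0.8 up to 1.2 g/kg per 30 days will be allowed up to 6 months". It adds that variable regimens are expected and that, for patients who are not significantly declining, "efforts will be made to continue treatment regimens already instituted".

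Section 6.0 (IVIg infusions) has two dosing paragraphs.

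- **Treatment-naive patients** receive a 2 g/kg load. After that: "Patients will then have 1 g/kg IVIg infusions scheduled every 3 weeks for 6 months".
- **Previously treated patients:** "They will resume according to the patient's previous schedule". The next sentence sets their limit: "Patients will have up to 1.2 g/kg monthly to account for different patient management schedules and variation".

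A later sentence in the same section says, without naming a group, that infusions are given every 3 weeks. Section 5.0 describes the study as observational, with therapy left unchanged.

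**The concern.** The ceiling for patients already on IVIg is lower than the maintenance dose that the study gives to patients it starts itself. Someone begun elsewhere a few months ago on exactly the study regimen falls inside the inclusion 1 window but outside the inclusion 2 dose range. The person screening that patient has three courses: exclude, enrol above the Section 6.0 limit, or lower the dose. The text does not choose between them, and lowering the dose runs against other sentences of the protocol.

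At stake are an unintended exclusion, an avoidable protocol deviation, or an unplanned change of therapy. Section 5.0 plans 20 recruits for 10 completers, and the protocol's background puts prevalence at 1 to 9 per 100,000. Even one eligible patient lost to an unintended limit would be noticed.

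**Working it through.** **Inputs.** Ceiling: 1.2 g/kg per 30 days (Section 4.0, inclusion 2) and 1.2 g/kg monthly (Section 6.0, previously treated). Maintenance: 1 g/kg every 21 days (Section 6.0, treatment-naive). Load: 2 g/kg (same paragraph).

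**What the ceiling permits.** The protocol gives no derivation of 1.2, so it can only be translated.
- At a 21-day interval: 1.2 × 21/30 = 0.84 g/kg per infusion.
- At 1 g/kg per infusion: 30/1.2 = 25 days between infusions.
- For comparison, 1 g/kg every 28 days is 30/28 = 1.07 g/kg per 30 days, which fits.

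**The study's maintenance regimen on the same scale.** Dose per month = g/kg per infusion × days in month / interval.

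| Month length | 1 g/kg every 21 days |
|---|---|
| 28 days | 28/21 = 1.33 |
| 30 days | 30/21 = 1.43 |
| 30.44 days | 30.44/21 = 1.45 |
| 31 days | 31/21 = 1.48 |

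All exceed 1.2. At 30 days the excess is 1.4286/1.2 − 1 = 19%.

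**Averaging over the study period.** With the load at day 0, maintenance infusions fall on days 21, 42, …, 168, which is 8 in 180 days. The average is 8 × 30/180 = 1.33 g/kg per 30 days without the load and (2 + 8) × 30/180 = 1.67 with it. Neither fits.

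**What compliance would require of an admitted patient on 1 g/kg every 3 weeks.** Either the dose falls to 0.84 g/kg (a 16% cut) or the interval stretches to 25 days. The first changes therapy. The second abandons the previous schedule.

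**Why the bound needs a definition as well as a higher number.** Infusions on days 1 and 22 fall in one 30-day window, so a literal count gives 2 g/kg for a regimen that averages 1.43. The load plus the first maintenance dose gives 2 + 1 = 3 g/kg in the first 30 days. A patient recently loaded elsewhere would fail even a raised bound if the load were counted.

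**The case against.** Three arguments deserve weight.

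**The text is flexible.** Inclusion 2 goes straight on to expect variable regimens and to favour continuing them, and no exclusion criterion names an IVIg dose. An investigator could take this as discretion to enrol at 1.43. That reading is possible, but neither sentence names a higher dose or waives the range. Section 6.0 presents 1.2 as the allowance that already covers variation between schedules. The flexibility therefore leaves the conflict unresolved.

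**The difference may be deliberate.** The naive regimen follows a load, while the 1.2 limit is for patients under other physicians' care, and nothing says the two must match. This cannot be excluded. But the protocol gives no reason for holding treated patients below a maintenance dose it gives to others, and a deliberate limit would still collide with continuing established regimens.

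**It may affect nobody.** Section 5.0 states: "All efforts will be made to recruit patients prior to therapy initiation without significantly delaying therapy". This stands, and it keeps the severity low.

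A reader might also infer that the protocol orders treated patients' doses to be cut at entry, or leaves that open. It does not: no sentence orders a cut, and the statements on unchanged therapy and resumed schedules point the other way. Nor does inclusion 2 put the study's own naive patients in breach. Its reference to regimens already under way, and the separate naive regimen in Section 6.0, show that it concerns patients already on IVIg.

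**Conclusion.** The point holds as a minor internal contradiction in an eligibility and dosing rule. The study's maintenance dose is 1.43 g/kg per 30 days against a ceiling of 1.2, and no month length between 28 and 31 days reconciles them. The conclusion assumes that the 1.2 figure is applied as written and that some candidates arrive on 1 g/kg every 3 weeks. How many would do so is not given and may be none.

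No sample size, error rate or test is affected. A reader might go further and infer that the Aim 2 signed-rank tests are compromised because naive and previously treated patients start from different baselines. The documents do not support that as part of this point. Section 10.0 does not mention the two groups, within-patient comparisons remain valid, and summaries by prior treatment are commonly left to a statistical analysis plan, which is not at hand.

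**What to change.** Make three small changes to the text.

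1. **Inclusion 2 (Section 4.0):** raise the upper bound from 1.2 to 1.5 g/kg per 30 days. Define it as average maintenance dose, g/kg per infusion × 30 / interval in days, with any loading dose not counted.
2. **Previously treated paragraph (Section 6.0):** use the same bound and definition. The figure of 1.5 covers the study regimen even if a month is taken as 31 days (1.48).
3. **General 3-weekly infusion sentence (Section 6.0):** limit it to treatment-naive patients, so that previously treated patients keep their own interval.

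The cost is a short amendment. Some previously treated patients may then receive more than 1.2 g/kg per 30 days. A patient on 1 g/kg every 3 weeks would be at the maintenance dose the study already gives naive patients. The bound itself sits slightly above that dose (1.5/1.4286 = 1.05, or 5%). If even that margin is unwelcome, 1.43 under the 30-day formula is the lowest two-decimal figure that admits the study's own regimen.
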